### **Key Secondary Efficacy Outcome Variables and Analyses**

Multiplicity adjustment will be performed across all secondary endpoints.

Progression-free survival will be compared between the pirfenidone 2403 mg/d and placebo groups using the log-rank test. A proportional hazards model will be used to estimate the hazard ratio. Descriptive analysis of progression free survival will be presented using Kaplan-Meier curves. Mortality will be analyzed using logistic regression with a treatment effect and accounting for potential over- or under-dispersion in the outcome.

The slope for annual rate of FVC decline will be analyzed using a random coefficient regression model with treatment and baseline FVC as covariates.

DLCO will be analyzed using a rank linear regression model with the rank change in %DLCO

from Baseline to Week 52 as the outcome variable and rank Baseline %DLCO and HP therapy as covariates.

Non-elective hospitalization from any cause and CT progression of fibrosis will be compared between the pirfenidone 2403 mg/d and placebo groups using logistic regression accounting for possible over- or under-dispersion in the outcome.

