### *Key Secondary Efficacy Outcome Variables*

1. Progression-free survival (PFS) defined as the time from study treatment randomization to the first occurrence of any of the following events:
  - a. Relative decline from baseline in  $\geq 10\%$  in FVC and/or DLCO
  - b. Acute exacerbation of FHP defined as acute respiratory declined leading to hospitalization or ER or Urgent care evaluation; or evidence of all of the following criteria within a 4-week period in the outpatient setting:
    - i. Increase from baseline  $\text{FIO}_2 \geq 1 \text{ L O}_2$ .
    - ii. Clinically significant worsening of dyspnea and/or cough.
    - iii. New, superimposed ground-glass opacities or consolidation or new alveolar opacities on chest x-ray or CT.
    - iv. Primary: if all other causes excluded (e.g., acute gastro-esophageal aspiration, pneumothorax, infection, left heart failure, pulmonary

embolism, or identifiable cause of acute lung injury).

- c. A decrease from baseline of at least 50 meters in 6-minute walk distance.
- d. Change in background therapy (need for a new course of PO or IV steroids or for the patient receiving maintenance prednisone, as a need to increase the dose by 10 mg or more; and/or addition of cyclophosphamide, azathioprine, mycophenolate mofetil or mycophenolic acid).
- e. Death

2. Slope of FVC over 52-week treatment period.
3. Mean change in %DLCO at week 52
4. Proportion of patients with all-cause mortality.
5. Proportion of patients with all-cause hospitalization.
6. Proportion of patients with hospitalization for respiratory cause.
7. Proportion of patients with respiratory exacerbations requiring hospitalizations.
8. Proportion of patients with evidence of progression in fibrosis on visual comparison of baseline and week 52 HRCT scans.

*Exploratory Outcome Variables:*

1. Mean change from baseline in health-related quality of life, measured by St. George's Respiratory Questionnaire (SGRQ) (3 domain scores and total score), at Week 52.
2. Mean change from baseline in health-related quality of life, measured by A Tool to Assess Quality of Life Questionnaire (L-IPF) at Week 52.
3. Mean change from Baseline to Week 52 in dyspnea as measured by the University of California at San Diego Shortness-of-Breath Questionnaire (UCSD SOBQ) score.
4. Proportion of patients with evidence of progression, stability or improvement in fibrosis on texture-based quantitative analysis of CT.

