## **STATISTICAL METHODS**

### **Randomization and Treatment Assignment**

In this double-blind study, subjects will be randomized to receive either pirfenidone 2403 mg/d or placebo in a 2:1 ratio.

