## **Efficacy Analyses**

### **Primary Efficacy Outcome Variable and Analysis**

The primary efficacy analysis will estimate the mean rank change in %FVC from Baseline to Week 52. Data will be analyzed using a rank linear regression model with the rank change in %FVC from Baseline to Week 52 as the outcome variable and rank Baseline %FVC and HP therapy (placebo or pirfenidone) and concomitant immunosuppressive therapy as covariates. The treatment effect will be tested using the Wald test.

The primary efficacy analysis will be tested at an alpha level of 0.05. Missing data due to reasons other than death will be replaced with imputed values using the MICE method (multiple imputation via chained equations). Missing data due to lung transplant will be imputed using the MICE method even if the subject dies after lung transplant.

Subjects with missing assessments due to death will be ranked worse than those who remain alive. Subjects who die will be ranked according to the time until death, with the shortest time until death as the worst rank.

Supportive analyses of the primary efficacy outcome will include the following:

1. Landmark analyses of mean change in %FVC from Baseline to Weeks 13, 26, 39 and 52.
2. Mean rank change in %FVC compared to Baseline across all study time points using a rank linear mixed effects model for repeated measures.

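### Background immunosuppression is a covariate in the primary %FVC model but not in the %DLCO, FVC-slope or PFS analyses: a gap in consistency and precision on secondary endpoints, not a built-in bias

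*Combined protocol and SAP*

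**What the plan says.** All references are to the combined protocol and SAP.

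- **Primary model** (Primary Efficacy Outcome Variable and Analysis): the rank regression of %FVC change uses "rank Baseline %FVC and HP therapy (placebo or pirfenidone) and concomitant immunosuppressive therapy as covariates". This also fixes the meaning of HP therapy: it is the randomized treatment, not background immunosuppression.
- **%DLCO** (Key Secondary Efficacy Outcome Variables and Analyses): a parallel rank regression, with rank change "from Baseline to Week 52 as the outcome variable and rank Baseline %DLCO and HP therapy as covariates". Immunosuppression is not listed.
- **FVC slope** (same section): a "random coefficient regression model with treatment and baseline FVC as covariates". Immunosuppression is not listed.
- **PFS** (same section): "Progression-free survival will be compared between the pirfenidone 2403 mg/d and placebo groups using the log-rank test", with no strata named. For estimation, "A proportional hazards model will be used to estimate the hazard ratio", with no covariates named.
- **PFS event rule** (Study Endpoints, key secondary item 1d): a change in background therapy is an event. A new oral or intravenous steroid course counts; "for the patient receiving maintenance prednisone, as a need to increase the dose by 10 mg or more"; and so does adding any of four listed immunosuppressants.
- **Randomization** (Randomization and Treatment Assignment): "subjects will be randomized to receive either pirfenidone 2403 mg/d or placebo in a 2:1 ratio". Neither this section nor Study design, Randomization and Blinding, or the Day 1 randomization step mentions a stratification factor.
- **Permitted background therapy** (Concomitant Medications): prednisone, azathioprine, mycophenolic acid and mycophenolate mofetil.

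**The concern.** The plan treats background immunosuppression as important enough to adjust for in the primary analysis, then omits it, without giving a reason, from two closely related lung-function analyses in the same patients. Background Information gives grounds to expect it to be prognostic: it says that immunomodulators are usually started once clinically significant progression is recognized.

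For PFS there is a second route. What counts as a component d event depends on starting therapy. A patient on maintenance prednisone has a dose-increase criterion, a patient not on steroids qualifies by a new course, and a drug already being taken cannot be added.

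If the arms differ by chance in background therapy, the secondary estimates would carry that difference while the primary estimate would be adjusted for it. Deciding after unblinding whether to adjust would leave a choice between two sets of results.

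**Working it through.** The plan gives no figure on this point, so there is none to reproduce. The check has three parts.

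**1. Covariate lists side by side**

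| Analysis | Baseline value | Treatment | Immunosuppression |
|---|---|---|---|
| %FVC rank model (primary) | yes | yes | yes, called *concomitant* |
| %DLCO rank model | yes | yes | not in the list |
| FVC slope model | yes | yes | not in the list |
| PFS log-rank test | – | yes | no strata named |
| PFS proportional hazards model | none named | yes | none named |

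For %DLCO and slope the list is explicit and omits the factor. For the proportional hazards model the text is silent.

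**2. Chance imbalance**

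Inputs: 42 patients randomized 2:1 (Sample Size and Power Considerations), so 28 and 14. Assumption: K of the 42 are on background therapy at Day 1, with K from 15 to 30 (15/42 = 36%, 30/42 = 71%).

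Without stratification, the number X on therapy in the placebo arm is hypergeometric (42 patients, K on therapy, 14 drawn). The gap is X/14 − (K − X)/28.

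Example, K = 21: X = 9 gives 9/14 − 12/28 = 64.3% − 42.9% = 21.4 points, and X = 5 gives the mirror image. P(X ≤ 5) + P(X ≥ 9) = 16.3% + 16.3% = 32.6%.

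| K | Share on therapy | P(gap of at least 20 points, either direction) |
|---|---|---|
| 15 | 36% | 30.6% |
| 21 | 50% | 32.6% |
| 26 | 62% | 18.0% |
| 29 | 69% | 15.9% |
| 30 | 71% | 27.7% |

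Over every K from 15 to 30 the range is 15.9% to 32.6%. The gap can take only a coarse set of values with arms this small, so the probability jumps. It is 28% to 33% when K is a multiple of 3 and about 16% to 19% otherwise. In one given direction it is about 6% to 16%.

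**3. What an imbalance does to PFS**

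Assumption: background therapy multiplies the PFS hazard by h. A 20-point gap then shifts the unadjusted hazard ratio by roughly exp(0.2 × ln h):

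- h = 1.5: 1.08
- h = 2: 1.15
- h = 3: 1.25 (slightly high; a simulation with 60% versus 40% on therapy and about 50% event risk gave 1.22)

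The unstratified and stratified log-rank tests were compared by simulation: 4,000 trials per setting, 28/14 patients, half on background therapy, 50% one-year event risk at the average hazard, two-sided 5%. Apart from the arm sizes, these settings are assumptions.

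| Setting | Unstratified | Stratified |
|---|---|---|
| Type I error, h = 1 | 5.6% | 5.6% |
| Type I error, h = 2 | 5.3% | 5.5% |
| Type I error, h = 3 | 4.7% | 4.7% |
| Type I error, h = 3, only trials with a gap of at least 20 points | 7.1% | 5.4% |
| Power at treatment HR 0.4, h = 1 | 41.6% | 40.4% |
| Power at treatment HR 0.4, h = 2 | 41.1% | 41.5% |
| Power at treatment HR 0.4, h = 3 | 37.4% | 40.4% |

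The two tests differ materially only at h = 3, and then by about 3 points of power.

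**The case against.** Several objections stand and limit the point.

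- **An unstratified log-rank test is valid in a randomized trial.** Overall type I error is about 5%. A reader might infer that the secondary comparisons are biased by design; they are not. Randomization balances the factor on average, and the issue is what happens in one small trial.
- **No background group is barred from component d.** A reader might infer that some patients cannot have such an event. A patient on prednisone can qualify by a dose increase, and one on azathioprine by a new steroid course or a different added agent. Component d is also one of five; the definitions of the other four do not refer to background therapy.
- **A yes/no factor does not match the drug-specific rule.** Patients on prednisone and on azathioprine fall in the same category although their criteria differ. Adjustment therefore deals with prognosis better than with the event definition.
- **Silence is not exclusion.** The documents do not say that randomization is unstratified or that the proportional hazards model has no covariates. They name none.
- **The plan already offers some protection.** Slope adjusts for baseline FVC and %DLCO for its baseline rank. Patients whose immunosuppression was started or escalated within one month are excluded (Medication Exclusions, item 19). Baseline medications are summarized by arm, so an imbalance would be seen.
- **Disagreement between %FVC and %DLCO would not become uninterpretable.** The two endpoints can differ under identical covariates. Mismatched lists only add one avoidable explanation.

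These objections do not remove the explicit difference between the primary, %DLCO and slope covariate lists, for which the plan gives no reason.

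**Conclusion.** The point holds as a matter of consistency and precision on secondary endpoints. The %DLCO and slope models omit a covariate that the primary model includes, and no adjustment is named for PFS although component d depends on existing therapy. The chance of a gap of at least 20 points between arms is about 16% to 33%. That rests on no stratification and on an assumed 36% to 71% of patients on background therapy.

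The effect on PFS is small unless background therapy is strongly prognostic. At an assumed hazard factor of 3, power is about 37% unstratified versus 40% stratified; at a factor of 2 or less the tests are within about 1 point. The documents give neither the prevalence nor the strength or direction of the association, so these sizes are illustrations.

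One related ambiguity should be settled at the same time. The primary covariate is called concomitant, which could be read as use during the study. Such use arises after randomization, and its changes are themselves PFS events, so the models align only if the covariate is Day 1 status throughout.

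**What to change.** Before unblinding, amend the SAP wording as follows.

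1. Define one covariate: immunosuppressive therapy at Day 1, yes or no. State that the primary model's concomitant therapy term means this status.
2. Add it to the %DLCO rank model.
3. Add it to the FVC slope model together with its interaction with time. A main effect alone adjusts the level of FVC, not its rate of decline.
4. Add it as a covariate in the PFS proportional hazards model. Keep the log-rank test as planned, or add a version stratified by Day 1 status as a sensitivity analysis.

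Making the stratified log-rank test primary for PFS, or stratifying the randomization, is debatable. At 36% on therapy the smaller placebo stratum would be expected to hold 14 × 15/42 = 5 patients, and at 71% it would hold 14 × 12/42 = 4. Neither step is needed to close the gap.

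The cost is one or two degrees of freedom per model. No new data are needed, because concomitant medications are already reviewed at screening and on Day 1.

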### Study design

This is a single-center, randomized, double-blind, placebo-controlled, efficacy and safety study of pirfenidone in subjects with FHP. Approximately 42 subjects will be randomized in a 2:1 ratio to receive pirfenidone 2403 mg/d or placebo for 52 weeks. The primary efficacy endpoint is the mean change in %FVC from Baseline to Week 52, to be analyzed using a rank linear model. Subjects will receive blinded study treatment from the time of randomization until the Week 52 Visit.

Eligible subjects, males and females, aged 18–80 years (inclusive) must have a confident or high-confidence diagnosis of FHP according to pre-specified criteria without evidence of an alternative diagnosis that may contribute to their interstitial lung disease. Subjects will be required to have a FVC  $\geq$ 40% and DLCO  $\geq$ 30% at screening.

Subjects will enter the Screening Period, which may last up to 30 days. In addition of brief periods of corticosteroid use for acute FHP exacerbation, subjects will be allowed to receive any other therapy for the treatment of FHP as per pre-specified criteria.

The dose of study treatment will be titrated over 4 weeks (2 weeks at 1 capsule TID; 2 weeks at 2 capsules TID; and 48 weeks at 3 capsules TID (2403 mg/d). Pirfenidone dose modifications or interruption will be allowed for safety or tolerability reasons at any time during the study.

Subjects will have a telephone assessment at Week 1 and 3, and an in-clinic assessment at day 1, weeks 5, 13, 26, 39, and 52. Subjects will be asked to complete an adverse event (AE) and dosing compliance diary between all visits. If subjects discontinue study treatment early for any reason, they will be asked to continue with all scheduled study procedures through Week 52.

A Safety officer will review all deaths and monitor subject safety during the study.

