### **HRCT Scans**

HRCT scans obtained within 4 months before the Screening period as part of the standard of care for a patient may be used to confirm eligibility, provided they meet all of the image acquisition and quality criteria required by the CT expert readers. All HRCT digital images are to be stored on a dedicated disk. The images will be anonymized using a tool developed by the Quantitative Imaging Laboratory at National Jewish Health. The Quantitative Imaging Laboratory will be tasked with interpretation, archiving, and quantitative analysis of the images. One thoracic radiologist with expertise in FHP will review the HRCT scans using an electronic score sheet. Data regarding the HRCT interpretation will be entered electronically

into the trial research's database and incorporated into the clinical database. Evidence of progression, stability, or improvement in fibrosis on temporally blinded visual comparison of baseline and week 52 HRCT scans will be documented on a five-point scale (much better, better, same, worse, and much worse).

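### The over- or under-dispersion adjustment has nothing to estimate in logistic models with one yes/no outcome per patient

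*Combined protocol and SAP*

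**What the plan says.** Under Key Secondary Efficacy Outcome Variables and Analyses, the plan gives this method for deaths: "Mortality will be analyzed using logistic regression with a treatment effect and accounting for potential over- or under-dispersion in the outcome". Non-elective hospitalization and CT progression of fibrosis are also to be compared "using logistic regression accounting for possible over- or under-dispersion in the outcome". Neither sentence says how dispersion is to be estimated, over what grouping, or which test follows. For mortality the only model term given is treatment; for the other two no covariates are listed. The same section promises that "Multiplicity adjustment will be performed across all secondary endpoints", without naming a method.

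The Study Endpoints section fixes the unit of each outcome:

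- "Proportion of patients with all-cause mortality"
- "Proportion of patients with all-cause hospitalization"
- "Proportion of patients with evidence of progression in fibrosis on visual comparison of baseline and week 52 HRCT scans"

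Two further statements bear on grouping. Study design: "This is a single-center, randomized, double-blind, placebo-controlled, efficacy and safety study of pirfenidone in subjects with FHP". HRCT Scans: "One thoracic radiologist with expertise in FHP will review the HRCT scans using an electronic score sheet".

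**The concern.** A single yes/no outcome with probability p has variance p(1 - p). Extra-binomial variation can be seen only when outcomes come in groups: several patients per center, several reads per scan, several events per patient. Here there is one center, one CT reader and one outcome per patient, and the plan defines no other grouping. The dispersion parameter is therefore not identifiable.

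Software will still return a number if asked for a scale factor, and that number multiplies the standard error of the treatment effect. Because the estimator is not named, it could be chosen after the results are known. At stake are the p-values and odds-ratio intervals for three kinds of secondary outcome.

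**Working it through.** **Inputs.** Sample Size and Power Considerations gives 38 evaluable patients (13 placebo, 25 pirfenidone), 10% attrition and about 42 randomized 2:1. The 42 reproduces: 38/0.9 = 42.2 and 38 × 1.1 = 41.8. At 2:1 this is 14 placebo and 28 pirfenidone. The documents give no event rates for these outcomes, so the rates and example tables below are assumptions. The model is intercept plus treatment, which is stated for mortality and assumed for the others. Counts are placebo first, then pirfenidone.

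**Pearson estimate.** For an arm with n patients, e events and p = e/n, the contribution is [e(1 - p)² + (n - e)p²] / [p(1 - p)] = n, whatever e is, provided 0 < e < n. Hence:

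- both arms with events and non-events: (14 + 28)/40 = 1.05, so the standard error is multiplied by √1.05 = 1.025;
- placebo arm without events: 28/40 = 0.70; pirfenidone arm without events: 14/40 = 0.35;
- with 13 and 25 patients: 38/36 = 1.056.

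In 296 simulated 14/28 trials with strongly varying patient-level risk and events in both arms, the estimate was 1.05 every time. It cannot detect what it is meant to measure.

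**Deviance estimate.** This is -2 Σ[e ln p + (n - e) ln(1 - p)] over the two arms, divided by 40, so it depends only on the event proportions. For independent patients at equal rates in both arms, excluding tables with an empty or full arm, its mean is:

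| Event rate | 5% | 10% | 20% | 30% | 40% |
|---|---|---|---|---|---|
| Mean deviance/df | 0.54 | 0.71 | 1.01 | 1.23 | 1.36 |

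It would be read as under-dispersion below about 20% and over-dispersion above. With data grouped by arm there are two rows and two parameters, so no residual degrees of freedom and no estimate at all. A sandwich standard error equals the model one in this model, so that reading also changes nothing.

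**Example 1: 3/14 and 1/28.** Odds ratio (1/27)/(3/11) = 0.14, log -1.997. SE = √(1/3 + 1/11 + 1/1 + 1/27) = 1.209. Deviance/df = 23.18/40 = 0.579, root 0.761.

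- Unscaled: z = 1.997/1.209 = 1.65, p = 0.099, 95% CI 0.013 to 1.45.
- Pearson: SE 1.239, p = 0.107.
- Deviance: SE 0.920, z = 2.17, p = 0.030, 95% CI 0.022 to 0.82.

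**Example 2: 8/14 and 7/28.** Odds ratio 0.25, SE 0.694, deviance/df = 50.61/40 = 1.265. The p-values are 0.046 unscaled, 0.051 Pearson and 0.076 deviance.

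**All tables with events and non-events in both arms** (13 × 27 = 351 for 14/28; 12 × 24 = 288 for 13/25), Wald test, verdicts changed by scaling:

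| Arms, level | Deviance: to significant / to non-significant | Pearson (all to non-significant) |
|---|---|---|
| 14/28, 0.05 | 4 / 14 | 4 |
| 14/28, 0.05/8 = 0.00625 | 4 / 12 | 4 |
| 13/25, 0.05 | 2 / 10 | 4 |

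The second row assumes Bonferroni over the eight listed secondary outcomes. An example there is 5/14 and 1/28, which moves from 0.020 to 0.0044.

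**Type I error at nominal 5%, 14/28, by enumeration** (Wald tests with an empty or full arm counted as non-significant):

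| Event rate | Unscaled Wald | Pearson | Deviance | Firth | Fisher |
|---|---|---|---|---|---|
| 5% | 0.2% | 0.2% | 1.2% | 0.9% | 0.9% |
| 10% | 1.0% | 1.0% | 3.7% | 2.3% | 1.9% |
| 20% | 2.5% | 2.0% | 3.0% | 4.6% | 2.9% |
| 30% | 3.4% | 2.7% | 2.2% | 5.2% | 3.4% |
| 40% | 3.8% | 3.4% | 2.1% | 4.5% | 3.8% |

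The deviance column peaks at 4.1%, near a 13% rate. A quasi-binomial F test, which the plan does not name, would reach 14.7% at a 5% rate.

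**The case against.** The wording is precautionary: the plan speaks of potential or possible dispersion, so an analyst could fix it at 1 and claim compliance. Of the plausible readings, Pearson scaling and the sandwich are practically inert. Only deviance scaling moves results, nothing in the plan points to it, and it does not push the Wald test above 5%. At a 10% rate its 3.7% is closer to nominal than the unscaled 1.0%. All of this stands and limits the importance.

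The table counts are not probabilities. Weighted by likelihood under equal rates, deviance scaling changes the 0.05 verdict in 1.0%, 2.7%, 1.7%, 1.4% and 1.7% of trials at rates of 5, 10, 20, 30 and 40%. Under assumed real effects the figure is larger: about 7% for 40% on placebo against 15% on pirfenidone, and 13% for 20% against 5%. Both main examples are also non-significant under every version at 0.00625; only tables such as 5/14 and 1/28 change there.

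The constant 1.05 needs a treatment-only model. With one irrelevant covariate added and no true dispersion, simulated Pearson values had a 95% range of 0.67 to 1.30 at a 10% event rate. That spread is noise, so a covariate does not rescue the clause. The 13/25 check suits CT progression better than mortality, since vital status is followed to Week 52 after early withdrawal.

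Finally, an empty arm is the larger practical problem for deaths. At 14/28, at least one arm has no events (or all events) in about 61% of trials at a 5% rate and 27% at 10%. That is correct, and deleting the dispersion clause does not solve it.

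**Conclusion.** The concern holds. The plan twice calls for an adjustment that its own endpoints, single center and single CT reader leave no way to estimate. Under Pearson scaling with a treatment-only model and events in both arms, the effect is a standard error 2.5% larger. Under deviance scaling, intervals narrow or widen with event frequency alone, and a secondary verdict can change in either direction. There is no inflation above 5% with a scaled Wald test.

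The size is modest. Only secondary p-values and odds-ratio intervals are affected; the primary analysis and sample size are not, and deaths are reported as a safety outcome in any case. The identifiability argument needs no assumed event rates; the examples and error rates do, along with a treatment-only model for hospitalization and CT progression.

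**What to change.** Delete both dispersion clauses, state that dispersion is fixed at 1, and keep the planned logistic regression. This should be done before unblinding.

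Separately, name a fit and test that work when an arm has no events, where the maximum-likelihood odds ratio is zero or infinite. One choice is Firth penalized likelihood with a penalized likelihood-ratio test and profile interval:

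| Placebo, pirfenidone | Firth odds ratio (95% CI) | p |
|---|---|---|
| 3/14, 1/28 | 0.18 (0.016 to 1.23) | 0.081 |
| 8/14, 7/28 | 0.27 (0.068 to 0.974) | 0.045 |
| 4/14, 0/28 | 0.041 (0.0003 to 0.43) | 0.005 |

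Fisher's exact test is acceptable but more conservative. Power for an assumed 40% on placebo against 15% on pirfenidone is 43.6% with Firth, 42.6% with the unscaled Wald test and 35.8% with Fisher. The price of Firth is a type I error that reaches 5.2% at a 30% event rate.

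In the same edit, reconcile the hospitalization outcome: the endpoint list counts all admissions, while the analysis section restricts to non-elective ones.

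The cost is SAP wording only, with no change to patients, visits or sample size.
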